4.3.2 Clinical Laboratory Data

Clinical laboratory measure recorded over the course of the study will be summarized as defined in [Table 17](#).

Table 17. Clinical Laboratory Summaries

Endpoint	Description	Timing	Summary Method
Descriptive	Summary of Laboratory Category and Parameter (SI Units) at Screening Visit	Screening	Continuous Summary

4.3.3 Vital Signs Parameters

Vital signs endpoints will be defined and summarized as described in [Table 18](#).

Table 18. Vital Signs Summaries

Endpoint	Description	Timing	Summary Method
Descriptive	Summary Vital Sign measures at each timepoint measured plus Change from baseline	Day 1, Day 15, Day 28 (EOT)	Continuous Summary

4.3.4 Physical Examination

Clinically significant physical examination results for all subjects will be presented in a data listing for the Safety Population.

5. CHANGES FROM ANALYSES PLANNED IN THE PROTOCOL

The following analyses differ compared to those specified in the study protocol:

- All continuous data, regardless of normality, will be presented as number, mean, standard deviation, and range. Protocol had stated continuous, non-normally distributed data would be presented as number, median, interquartiles, and range.
- [Section 11.3.4 of the Protocol](#) states that change from baseline will be calculated for clinical laboratory evaluations. Clinical labs were only taken at screening and therefore, no change values will be calculated.
- The following secondary efficacy endpoints have been renamed:
 - ‘Change from baseline in abdominal distension at week 2’ will now be referred to as ‘change from baseline in abdominal girth at week 2’
 - ‘Change from baseline in maximal abdominal distension at week 4’ will now be referred to as ‘change from baseline in maximal abdominal girth at week 4’
 - ‘Change from Baseline in digestive sensations at weeks 4 and 8’ was an error as the study is only 4 weeks in duration. This should have been ‘Change from baseline in digestive sensations at week 2 (Visit 6) and week 4 (Visit 8)’.
 - ‘Change from baseline in Bristol Stool Form Scale at weeks 4 and 8’ was an error as the study is only 4 weeks in duration. This should have been ‘Change from baseline in Bristol stool form scale at week 2 (Visit 6) and week 4 (Visit 8)’.
 - Change from baseline in Bristol Stool Form Scale at Weekk 2 and 4 will be analyzed using linear mixed models with appropriate contrasts. The Protocol had previously specified generalized estimating equations (GEE) would be used for analysis.
- The HADS and IBS-SSS were assessed at Screening and EOT. These values will not be analyzed.

- **Section 11.3.3.5 of the Protocol** reports additional analysis that will be conducted. Specifically, it states, “The relationship between the hourly digestive sensation scores for bloating and the corresponding hourly difference in girth measures from hour 1 over the relevant time period during each of the two 24-hour periods at visit 4 and visit 8 will be assessed using longitudinal regression analysis.” This analysis will no longer be conducted.
- Given that the study was terminated by the sponsor after only 20 patients were randomized, there will be no formal statistical modeling (ANCOVA, MMRM) and descriptive statistics and confidence intervals will be presented only.

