11.3.3.2 Primary Efficacy Analysis

Changes in girth from the first hour of the 24-hour AIP at Visit 8 will be compared between the linaclotide and placebo groups with the AUC measure, adjusting for the corresponding changes in girth at Visit 4 and any other important confounding factors (such as age and BMI), using analyses of covariance.

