3. INTRODUCTION

[figure not shown]
This statistical analysis plan (SAP) provides a more technical and detailed elaboration of the statistical analyses of the efficacy and safety data as outlined and/or specified in the final protocol of Study MCP-103-403-P-04 ([Amendment 3](#), dated April 25, 2017). Specifications for the tables, figures, and data listings are contained in a separate document.

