4.1.1 General Methods

Distribution of study parameters and covariates will be summarised depending on the type of variable with the number of subjects and the number of missing data (where relevant).

Verification of the normality of the distribution for continuous data will be carried out by graphical inspection and consideration of skewness and kurtosis measures.

Percentages will be based on the total number of non-missing values. The number missing will be presented, but without a percentage.

Descriptive statistics will be presented as;

- Discrete data: number and percentage of participants in each category
- Ordinal categorical data: number and percentage of participants in each category, median, interquartiles, range
- Continuous data: number, mean, median, standard deviation, minimum, maximum

All confidence intervals reported will be two-sided and at the 95% confidence level. There is no adjustment for multiplicity.

If not otherwise specified, the baseline value is defined as the last nonmissing value measured before administration of study drug on Day 1.

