4.1.1.3 Statistical Methods

For descriptive summaries, N will represent the total number of patients within the summarized population and n will represent the number of non-missing patients for the summarized endpoint. All summary statistics will be presented by treatment and based on non-missing endpoint values, unless otherwise specified.

Table 2. Statistical Methods

Method	Definition
Categorical Summaries	
Number and percent of patients in each category
Percent based on number of non-missing valuesNumber of missing patients in each category; percent not presented.
Continuous Summaries	
Number of non-missing patients, mean, median, standard deviation, minimum, maximum

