4.1.3 Efficacy

4.1.3.1 Analysis of Primary Efficacy Endpoint

Baseline abdominal girth (as measured by AIP AUC) will be calculated using the first 24 hours of measurements from the belt following the Baseline Visit. If an AIP increase of >4 cm is not observed over the first 24-hour period, then baseline will be defined as the 24 hours leading up to the Randomization Visit on day 1. For subjects with an AIP increase of >4 cm in both 24 hour periods, the first 24-hour period will be used.

Table 13. Primary Efficacy Analysis

Endpoint	Description	Timing	Summary Method
Change from baseline in abdominal girth at Week 4	
The mean change from randomization (Visit 4) to the end of the study (Visit 8) in abdominal girth (as measured by AUC) determined by 24-hour AIP (with hourly averages), between the linaclotide and placebo groups.
 
The AUC will be calculated using the Trapezoidal method from the first reliable hour of measurement to last measurement (bedtime). The AUC for each patient will be then individually standardised by dividing the total AUC over the period by that patient's number of hours of measurement included in the AUC.
 
In case of missing data in the middle of the valid period of measurement, AUC is calculated with linear interpolation.
	Day -1 to Day 27	Continuous summary, 95% CI

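### After the stop at 20 randomised, the SAP drops the baseline-adjusted primary comparison and does not say whether the remaining 95% CI is for each arm or for the linaclotide-placebo difference

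*SAP*

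**What the plan says.** Protocol 11.3.3.2 compares the arms on the Visit 8 AUC measure by analysis of covariance, "adjusting for the corresponding changes in girth at Visit 4 and any other important confounding factors (such as age and BMI" being the adjustment, so the covariate list is open-ended.

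The last bullet of SAP Section 5 openly withdraws this because only 20 were randomised: "there will be no formal statistical modeling (ANCOVA, MMRM) and descriptive statistics and confidence intervals will be presented only". For the primary endpoint, SAP Table 13 leaves a continuous summary and a 95% CI. Four places bear on what that CI covers:

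- SAP 4.1.1.3 points to one interval per arm: "All summary statistics will be presented by treatment and based on non-missing endpoint values, unless otherwise specified". Its Table 2 definition of a continuous summary contains no CI.
- The endpoint text in SAP Table 13 points to a contrast: the change is "determined by 24-hour AIP (with hourly averages), between the linaclotide and placebo groups".
- SAP 4.1.1 fixes level and sidedness only: "All confidence intervals reported will be two-sided and at the 95% confidence level".
- SAP Section 3 places the layouts elsewhere: "Specifications for the tables, figures, and data listings are contained in a separate document".

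On baseline, SAP 4.1.3.1 uses the qualifying recording: "If an AIP increase of >4 cm is not observed over the first 24-hour period, then baseline will be defined as" the 24 hours before the Randomisation Visit.

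Section 5 also says that the Bristol Stool Form Scale change "will be analyzed using linear mixed models with appropriate contrasts". That conflicts with the no-modelling bullet in the same section and with the Table 14 row, which lists only a summary and a CI.

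**The concern.** The stated objective is the effect of linaclotide, so the primary table needs a defined linaclotide-minus-placebo estimate. As written, two programmers could produce different primary tables and both comply.

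If the interval is per arm, the mean change mixes any drug effect with regression to the mean. Participants enter because a recording showed a rise above 4 cm, and that recording is the starting point of the change. An arm can appear to improve with no drug effect. A between-arm difference, adjusted or not, removes this in expectation.

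If the interval is for the unadjusted difference, bias is not the issue. What is lost is some precision and protection against chance baseline imbalance, which is more likely to be material with about 10 per arm.

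A small sample is a fair reason to drop a hypothesis test. It is not in itself a reason to drop the adjusted estimate, since the SAP still intends to estimate with confidence intervals.

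**Working it through.** **Inputs from the documents.** Target difference 2.2 cm, SD 2.4 cm, two-sided 5%, 20 per group, 15% dropout, 20 randomised (SAP 4.2); 1:1 allocation (SAP 3.1).

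**Assumptions.** 10 per arm; SD 2.4 cm for the AUC at each visit; baseline/follow-up correlation ρ of 0.3, 0.5 or 0.7; 40-80% passing the girth cut; correlation c between the entry variable and baseline AUC of 0, 0.7 or 1; no drug effect. The second belt fitting is not modelled.

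**1. The plan's own figure.** The exact two-sample t-test gives 78.5% power at 19 per arm and 80.6% at 20, so the planned size reproduces. At 10 per arm, power for 2.2 cm is 49%.

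**2. The two readings of the CI.** Taking 2.4 cm as the SD of the analysed change:

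- per arm: t(9) × 2.4/√10 = 2.262 × 0.759 = 1.72 cm half-width;
- difference: t(18) × 2.4 × √(2/10) = 2.101 × 1.073 = 2.25 cm half-width.

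**3. Drift within an arm.** Expected mean change = −(1−ρ) × c × λ × 2.4, where λ is the mean of a standard normal above the entry cut (0.966 if 40% pass, 0.350 if 80% pass). For ρ = 0.5, c = 0.7 and 40% passing: 0.5 × 0.7 × 0.966 × 2.4 = 0.81 cm fall.

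**4. Simulation, 20,000 trials per cell.** Ranges run over pass rates from 80% to 40%.

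| Scenario | ρ | Arm mean change (cm) | Arm CI excludes zero | Adjusted CI narrower than change-score CI |
|---|---|---|---|---|
| A: c = 0 | 0.3 / 0.5 / 0.7 | 0 | 5% | 16% / 10% / 5% |
| B: c = 0.7 | 0.3 | −0.4 to −1.1 | 7-23% | 11-13% |
| | 0.5 | −0.3 to −0.8 | 6-17% | 7-8% |
| | 0.7 | −0.2 to −0.5 | 6-12% | 2-3% |
| C: c = 1 (upper end) | 0.3 | −0.6 to −1.6 | 10-46% | 4-10% |
| | 0.5 | −0.4 to −1.2 | 8-32% | 2-6% |
| | 0.7 | −0.25 to −0.7 | 7-20% | about 0% |

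The unadjusted between-arm difference stays within 0.03 cm of zero with about 95% coverage in every cell. The adjusted difference also has about 95% coverage.

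**5. Precision, closed form (scenario A).** Width ratio = √[((1+ρ)/2) × (N−3)/(N−4)] × t(N−3)/t(N−2). At N = 20 and ρ = 0.5: √(0.75 × 17/16) × 2.110/2.101 = 0.896. At ρ = 0.3 and 0.7 it is 0.835 and 0.954. At N = 17 (20 × 0.85) the ratios are 0.842, 0.904 and 0.963. Setting the ratio to 1 gives a break-even ρ of about 0.87 at N = 20 and 0.83 at N = 17.

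**6. Degrees of freedom.** An intercept, treatment and one covariate leave 20 − 3 = 17, or 17 − 3 = 14 after dropout.

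**7. Chance imbalance.** One standard error of the baseline difference is 2.4 × √(2/10) = 1.07 cm without truncation. It shifts the unadjusted change contrast by (1−ρ) × 1.07 = 0.75, 0.54 or 0.32 cm.

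**The case against.** **The withdrawal is disclosed and reasoned.** True, and no figure in the documents is wrong. But the stated reason supports dropping the test more than the estimate.

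**A between-arm CI is the more natural reading of Table 13.** The row names both groups, and the by-treatment rule applies to descriptive summaries, whose definition has no CI. This has force. Yet the row repeats the protocol's endpoint definition and names no interval or method, and the maximal-girth and symptom rows of Table 14 lack even that wording.

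**The separate table specifications may settle it.** They may, and they were not available here. What the primary interval estimates still belongs in the SAP.

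**Harm is limited.** With n, mean and SD by arm, a reader can compute the unadjusted difference, and the placebo arm shows the same drift. The more misleading pattern, in which only the linaclotide interval excludes zero, occurs in 5-18% of trials in scenario B and 6-25% in C, against about 5% with no drift. That narrows the concern without removing it.

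**The gain from adjustment is modest.** In single trials the adjusted interval is the wider one in roughly 10-38% of cases in A and 22-64% in C. With truncation, the baseline SD and hence the imbalance shift shrink; in C the shift is 0.42-0.57, 0.30-0.41 and 0.18-0.25 cm for the three correlations. This stands.

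**The 46% is an extreme.** It needs a 40% girth pass rate and an entry variable identical to AUC. The plan's 60% failure rate also covers other criteria, and a second fitting is allowed, so the girth pass rate should exceed 40%. This stands; scenario C is an upper end only.

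**The 2.4 cm may be the SD of change.** The per-visit SD would then be 2.4/√(2(1−ρ)) = 2.03, 2.40 or 3.10 cm, and the drift and imbalance figures in cm would scale with it. The exclusion rates and width ratios do not depend on the SD.

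**Conclusion.** The concern holds and should be acted on. Two parts rest on the text alone: the protocol's adjusted comparison is withdrawn with no named between-arm replacement, and the SAP does not define what the primary CI estimates.

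The size depends on the reading. Per arm, the interval cannot answer the trial's question and would exclude zero too often with no drug effect: 6-23% in the middle scenario, up to 46% at the upper end, and 5% if entry and AUC are unrelated. For the unadjusted difference, coverage is sound. The case for adjustment is then an average 0-16% gain in width, plus protection against an imbalance shift of at most 0.75 cm per standard error of baseline difference, against a planned effect of 2.2 cm.

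The case against a per-arm interval is therefore the stronger part, and the case for baseline adjustment the weaker. The conflict over the stool-form model is secondary and probably leftover text.

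**What to change.** In SAP Table 13, and in the Week 2 and maximal-girth rows of Table 14:

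1. Keep the descriptive summaries by arm.
2. Add the linaclotide-minus-placebo difference from a linear model of the follow-up value on treatment and the corresponding Visit 4 value only, with a 95% CI and no p-value. This is a reduced form of the protocol's estimator and closes its open covariate list.
3. Label each CI as by-arm or between-arm, and state that by-arm intervals are not evidence of a treatment effect.

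Reword the last bullet of Section 5 to allow this one estimate, and reconcile it with the stool-form mixed-model bullet and the matching Table 14 row.

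The cost is SAP wording and one short model per girth endpoint, using a baseline already collected. The downsides are one degree of freedom, a linearity assumption, and little or no precision gain if the correlation is high or the entry rule strongly truncates baseline AUC. The adjusted interval would still be about ±1.6 to 2.2 cm: t(17) × 2.4 × √(1−ρ²) × √(2/10) gives 2.16, 1.96 and 1.62 cm at ρ = 0.3, 0.5 and 0.7, before about 3% more (√(17/16)) for estimating the slope. It should be presented as an estimate, not a test.

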4.2 SAMPLE SIZE JUSTIFICATION

A total of 40 (20 in each group) participants are required to complete the study, with 120 needed to enter screening to account for ineligible participants and dropouts.

To achieve 80% power to detect a difference of 2.2 cm or more (using a simple 2-sided t-test with estimated SD = 2.4 cm and the conventional 5% significance level) in the mean change in abdominal girth (as measured by AIP AUC) from the start to the end of the day, between the active and placebo groups, 20 participants per group (40 participants in all) are required. Assuming a 15% dropout rate, 47 participants would need to be randomised to yield 40 evaluable participants. Estimating a 60% screen/pretreatment failure rate (mostly from failure to meet distension criteria, but also pretreatment abdominal pain, abdominal bloating, and bowel movement criteria), 120 participants would need to enter screening to achieve 40 randomised participants.

Note: for a previous yogurt study, a mean difference in girth of 1.6 cm (SD = 2.4 cm) was observed

Sample size calculated using nQuery Advisor 3.0.

Note: Due to difficulties with enrollment, the study was terminated by the sponsor after 20 subjects were randomized.

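### The SAP drops the Visit 4-adjusted estimate of the primary girth endpoint because only 20 were randomised, but that number does not rule out a one-covariate adjusted difference with a 95% CI and no p-value

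*SAP*

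**What the plan says.** Protocol Section 11.3.3.2 compares the Visit 8 within-day girth AUC between linaclotide and placebo by analysis of covariance, "adjusting for the corresponding changes in girth at Visit 4". It leaves room for further covariates and names age and BMI as examples.

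SAP Table 13 (Section 4.1.3.1) defines the primary endpoint as the change in AUC from Visit 4 to Visit 8. Its summary method is "Continuous summary, 95% CI", with no covariate. The last bullet of SAP Section 5 gives the reason, which is termination after 20 were randomised, and the consequence: "there will be no formal statistical modeling (ANCOVA, MMRM) and descriptive statistics and confidence intervals will be presented only". The Week 2 and maximal girth rows of Table 14 carry the same summary method. No baseline-adjusted girth estimate remains in the SAP.

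The planning SD appears in SAP Section 4.2, "using a simple 2-sided t-test with estimated SD = 2.4 cm and the conventional 5% significance level", and is attached to a difference "in the mean change in abdominal girth (as measured by AIP AUC) from the start to the end of the day". Neither document states a correlation between the baseline and Week 4 measures.

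**The concern.** The stated reason does not lead to the action taken. With 20 participants a confirmatory test has little power, so leaving it out is sensible. Estimation is a different matter, and the SAP keeps confidence intervals. A model with arm and one baseline value has three parameters, and the baseline value is already collected from everyone randomised.

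Two things are at stake. The first is precision: this terminated trial will give one estimate of the girth effect, and raw change is usually the less precise estimator. The second is how the estimate reads in the trial that was actually run. Raw change fixes the baseline slope at 1. If the true slope is lower, a chance difference between arms at Visit 4 is subtracted too heavily and part of it appears, reversed, in the treatment difference. Allocation is by blocks with no stratification on girth (Protocol Section 7.3), so nothing in the design holds the arms level at baseline.

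**Working it through.** **Inputs from the documents.** SD 2.4 cm, target difference 2.2 cm, two-sided 5%, 20 per group planned (SAP 4.2). 20 randomised (SAP 4.2) at 1:1 (SAP 3.1), so about n = 10 per arm. Entry requires a girth increase above 4 cm (Protocol 5.1.1.3).

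**Assumptions.** Correlation ρ between baseline and Week 4 is not given, so a range is shown. SD is taken as 2.4 cm at both visits, and all 20 are taken to have Visit 8 data.

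**Step 1: the plan's own figure.** The SAP says "To achieve 80% power to detect a difference of 2.2 cm or more", "20 participants per group (40 participants in all) are required". The exact noncentral t calculation gives 80.6% power at 20 per group and 78.5% at 19. The stated number reproduces.

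**Step 2: expected 95% half-width of the between-arm difference, n = 10.**

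- Raw change: t(18) × 2.4 × √(2(1−ρ)) × √(2/n), with t(18) = 2.101.
- Adjusted for baseline only: t(17) × 2.4 × √(1−ρ²) × √((2/n)(17/16)), with t(17) = 2.110. The factor 17/16 is the average cost of estimating the covariate slope.

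At ρ = 0.5: raw 2.101 × 2.4 × 1 × 0.447 = 2.25 cm; adjusted 2.110 × 2.4 × 0.866 × 0.461 = 2.02 cm.

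| ρ | Raw change (cm) | Baseline-adjusted (cm) | Raw v adjusted |
|---|---|---|---|
| 0.3 | 2.67 | 2.23 | 20% wider |
| 0.5 | 2.25 | 2.02 | 12% wider |
| 0.7 | 1.75 | 1.67 | 5% wider |
| 0.85 | 1.24 | 1.23 | 0.4% wider |
| 0.9 | 1.01 | 1.02 | 1% narrower |

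A simulation of 20,000 trials at each of ρ = 0.3, 0.5, 0.7 and 0.9 agreed with the formulas, with coverage of about 95% for both methods. If 2.4 cm is instead the SD of the visit-to-visit change, the raw half-width is 2.25 cm at every ρ and the ratios are unchanged.

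**Step 3: break-even.** The two widths are equal when 2/(1+ρ) = (2.110/2.101)² × 17/16 = 1.0715, so ρ is about 0.87. At 8 per arm it is about 0.82. If age and BMI are added and are not prognostic, break-even at 10 per arm falls to about 0.60.

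**Step 4: narrowed baseline.** The entry rule may reduce the baseline spread. Hold the slope β and the residual SD, 2.4√(1−β²), as above, and let the baseline SD s_b fall (assumed values). The SD of raw change is then √(residual SD² + (1−β)² s_b²), and the adjusted width does not change.

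| Slope β | Adjusted (cm) | Raw, s_b = 1.8 | Raw, s_b = 1.2 |
|---|---|---|---|
| 0.3 | 2.23 | 2.46 (10% wider) | 2.29 (3% wider) |
| 0.5 | 2.02 | 2.13 (5% wider) | 2.03 (0.5% wider) |
| 0.7 | 1.67 | 1.69 (1% wider) | 1.65 (1% narrower) |

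**Step 5: chance imbalance in the realised trial.** The between-arm baseline difference has SD s_b × √(2/10): 1.07 cm at s_b = 2.4 and 0.54 cm at s_b = 1.2. A 1-SD imbalance shifts the raw-change difference by (1−β) times that amount, in the opposite direction. For β from 0.7 down to 0.3 the shift is 0.32 to 0.75 cm at s_b = 2.4, or 0.16 to 0.38 cm at s_b = 1.2. Adjustment for the Visit 4 value removes it if the relation is linear.

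**The case against.** The change is openly declared, with its reason, and descriptive reporting after termination at half the planned completers is a legitimate choice. Every half-width above for ρ from 0.3 to 0.7, adjusted or not, exceeds the 1.6 cm difference that SAP Section 4.2 quotes from the earlier yoghurt study. A gain of 0.08 to 0.44 cm, and less if the baseline is narrowed, is unlikely to change what the trial can conclude. All of that stands, and it keeps the point modest.

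Three stronger readings are tempting, and the documents do not support them.

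- A reader might infer that dropping the adjustment is certain to widen the interval. It is not: ρ is unknown, the entry rule may remove most of the gain, and against the protocol's model with age and BMI included the advantage goes above ρ of about 0.60.
- A reader might infer that raw change ignores baseline imbalance, or that its interval is invalid. Raw change subtracts the baseline in full, so it over-corrects when the slope is below 1, and its interval still covers at about 95%. Averaged over randomisations, the imbalance loss is the same loss as the wider interval. It is a separate matter only for the one allocation that occurred.
- A reader might infer that the planned 80% power is undermined. With no test planned and the trial stopped at 20, that has no consequence. The wording of Section 4.2 also does not settle beyond doubt which quantity the 2.4 cm describes.

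The objection does not justify the stated reason. Twenty participants can support one covariate. Another bullet of SAP Section 5 still assigns linear mixed models to the Bristol Stool Form Scale, which conflicts with the last bullet.

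**Conclusion.** The point holds in a limited form. The SAP removes the protocol's Visit 4-adjusted primary estimate for a reason that justifies leaving out a test but not leaving out the estimate. The expected loss in precision is 5% to 20% of interval width for ρ from 0.7 to 0.3 with SD 2.4 cm at both visits, 1% to 10% if the baseline SD is 1.8 cm, and about nil (3% wider to 1% narrower) if it is 1.2 cm. In the narrow-baseline case the main value of adjustment is that the realised difference is not shifted by a chance imbalance. These sizes rest on the assumed ρ, the equal or narrowed SDs, and 10 per arm with complete data.

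The comparison presumes a between-arm interval. Table 13 refers to the two groups, while SAP Section 4.1.1.3 presents summaries by treatment, so the SAP does not make clear that such an interval is planned. That is a separate gap, which the same edit would close.

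**What to change.** In Table 13, in the Week 2 and maximal girth rows of Table 14, and in the last bullet of Section 5, keep one model per girth endpoint: the post-baseline value on arm and the corresponding Visit 4 value only, with no age, BMI or other covariates. Report the adjusted linaclotide-minus-placebo difference with its 95% CI, labelled as estimation and without a p-value, and show raw change by arm beside it.

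The edit is one sentence in Section 5, three table rows and a few lines of code. The statistical price is one degree of freedom, a linearity assumption, and a slightly wider interval if the correlation is very high or the baseline spread is narrow.
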